2.3 Study design and conduct

Study ONC001 is a multicenter, nonrandomized, open-label, Phase 1/2 study evaluating the safety, PK, efficacy (as assessed by antitumor activity), PD, biomarkers, and immunogenicity (ADA activity) of intravenous (iv) UCB6114 as monotherapy and in combination with selected standard of care (SoC) regimens in study participants with advanced solid tumors.

The study has a modular design including up to 3 dose escalation modules (Parts A, B, and C), 1 dose adaptation module (Part A1), and up to 4 dose expansion modules (Parts D, E, F, and G). Depending on emerging data, not all modules may open. This SAP is focused only on the first dose escalation module of the study (Part A).

[figure not shown]
Part A consists of a Screening Period (28 days), a Treatment Period (consisting of 28-day cycles), an SFU visit (approximately 30 days after the last dose of study treatment) and a Final Visit (approximately 3 months after the last dose of study treatment). The planned duration of study treatment is 2 cycles. Participants may remain on study for additional cycles if they are receiving therapeutic benefit or until they fulfill one of the criteria for study discontinuation.

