Best overall response (BOR) is defined for each study participant as the best overall tumor response from each tumor assessment (scheduled and unscheduled assessments performed between Days 21 and 28 of every even cycle of study treatment) according to the RECIST criteria for changes in target and non-target lesions and the appearance of new lesions. Best overall response is determined from the start of study treatment until documented objective disease progression or the date of subsequent anti-cancer therapy (systemic therapy, surgery or radiotherapy for cancer), whichever occurs first. If anti-cancer therapy is started on the same day as a tumor assessment, then the overall response from that assessment will be used in the derivation of BOR. For a BOR of SD, a participant's tumor measurements must have met the SD criteria at least once after the start of study treatment at a minimum interval of no less than 6–8 weeks (42–56 days).

For Part A of this study, BOR determination requires confirmation of CR or PR responses at a subsequent assessment ≥ 4 weeks (28 days) after the criteria for CR or PR responses are first met. In addition, Table C in Appendix 10.9 of the protocol provides the derivation of BOR when confirmation of CR and PR responses are required. Confirmed BOR and unconfirmed BOR will be derived programmatically based on the overall tumor assessment data recorded on the eCRF

by the investigator and using the detailed guidance included in the Derivation of Efficacy Endpoints document Version 0.6 (dated 21 January 2022).

Duration of response (DOR) will be calculated for participants with a confirmed BOR of CR or PR as the time in days from the start date of the confirmed CR or PR to the first date that recurrent or progressive disease is objectively documented (i.e. according to the RECIST guidelines). This will be referred to as the duration of confirmed response and the following calculation will be performed:

$$\begin{aligned} & \text{Duration of Confirmed Response} \\ & = (\text{Date of First Objective Disease Progression} \\ & \quad - \text{Start Date of Confirmed CR or PR Response}) + 1 \end{aligned}$$

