For participants who die without objective disease progression, duration of confirmed response and duration of unconfirmed response will be censored on the date of death, regardless of cause. For a participant who discontinues early from Part A of the study with no objective disease progression, duration of confirmed response and duration of unconfirmed response will be censored on the date of their last available (scheduled or unscheduled) tumor assessment at which a lack of objective disease progression was determined. Participants who discontinue study treatment but who do not have documented objective disease progression (i.e. according to the RECIST guidelines), duration of confirmed response and duration of unconfirmed response will be censored at the date of their last available (scheduled or unscheduled) tumor assessment

at which a lack of objective disease progression was determined. Such participants might include those that are ongoing in Part A at the time of any defined data cut-off.

In the sensitivity analyses of duration of confirmed response and duration of unconfirmed response, the same censoring rules will apply except that the date of last contact will be used for the censoring of participants who discontinue early from Part A, complete Part A of the study or are ongoing in the study at a data cut-off for Part A without objective disease progression, clinical disease progression or death.

Date of last contact will be the latest of the dates of premature study termination and of last contact recorded on Study Termination eCRF page, the date of death, the date of last dose of study treatment, the dates of all visits, AE start and end dates (with partial dates imputed as earliest possible) and the date of contact recorded on the Survival Safety Follow-up and Survival Final Follow-up eCRF forms.

Further details on the derivation of duration of confirmed response and duration of unconfirmed response are included in the Derivation of Efficacy Endpoints document Version 0.6 (dated 21 January 2022).

Progression-free survival (PFS) will be calculated as the time in days from the first dose of study treatment to the date of the first documented objective disease progression (i.e. according to the RECIST guidelines), or death due to any cause, whichever occurs first. The following calculation will be performed:

$$PFS = (Date\ of\ Objective\ Progressive\ Disease/Death - Date\ of\ First\ Dose) + 1$$

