Participants who die due to any cause without a documented objective disease progression will be considered to have progressed on the date of their death. Participants who do not have any post-Baseline tumor assessments will be censored on the date of their first dose of study treatment. Participants who discontinue early from Part A or discontinue study treatment without documented objective disease progression or death, will be censored on the date of their last available (scheduled or unscheduled) tumor assessment at which a lack of objective disease progression was determined. Participants who start anti-cancer therapy during Part A without a prior documented objective disease progression will be censored on the date of their last available (scheduled or unscheduled) tumor assessment prior to the initiation of the subsequent anti-cancer therapy. If anti-cancer therapy starts on the same date as the participant's tumor assessment and determination of objective disease progression, or the participant's death (due to any cause), then the participant will not be censored and the participant will be included as having an uncensored event on this date. This censoring rule will also be applied to participants who are ongoing at any data cut-off for an analysis of Part A data who have no documented objective disease progression. The use of anti-cancer therapy during Part A will be identified via ongoing medical review of the concomitant medications together with the start dates of further anti-cancer therapy information recorded on the survival follow-up pages of the eCRF.

As a sensitivity analysis, PFS will also be calculated as the time in days from the first dose of study treatment to the date of the first documented objective disease progression (per RECIST 1.1), the date of clinical disease progression, as determined by the investigator, or the date of death due to any cause, whichever occurs first. Last contact date (as defined above for DOR) will be used for the censoring of participants still alive with no reported disease progression

(objective or clinical). The same rules described above for the censoring of participants who start anti-cancer therapy will be applied in this sensitivity analysis.

Further details on the derivation of PFS are included in the Derivation of Efficacy Endpoints document Version 0.6 (dated 21 January 2022).

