10.1.2 Analysis of the antitumor activity endpoints

The analyses of the antitumor activity endpoints in Part A will be performed for the PPS. As a sensitivity analysis, all analyses will be repeated for the SS. All listings will be presented for the SS. Summaries and listings will be presented by treatment group.

All lesion assessment data recorded at Baseline and during the Treatment Period (during every even cycle of study treatment) will be listed separately for target lesions, non-target lesions and new lesions. These listings will include lesion number and lesion type (nodal/non-nodal), location, method of assessment, dimension (or an indication that the lesion is too small to measure, for target lesions only) and lesion response evaluation (for non-target lesions at post-Baseline assessments). The listing for target lesions will also include the derived eCRF component data used for the determination of the overall target lesion response at each post-Baseline assessment (e.g. sum of all dimensions across target lesions and percentage change from Baseline in the sum). In addition, the overall response assessment for target lesions and non-target lesions, as determined by the investigator, will be listed together with the presence of new lesions and the investigator's overall tumor response assessment.

The investigator's overall tumor response assessment will be summarized using frequency counts and percentages by visit (tumor assessment). For the purpose of this summary, post-Baseline tumor assessments (scheduled or unscheduled but excluding tumor assessments performed at the SFU visit) will be assigned to the targeted Day 22 visit of each even cycle of study treatment using the protocol-defined window of Day 21 to 28 (± 2 days). For participants who receive 2 or more cycles of study treatment, post-Baseline tumor assessments that were performed on Day 19 to Day 30 relative to Day 1 of each even cycle will be included as Cycle 2/4/6/8 etc. Day 22 assessments. For participants who discontinue study treatment prior to the start of Cycle 2, post-Baseline tumor assessments that were performed on Day 47 to 58 relative to Day 1 of Cycle 1 will be included as a Cycle 2 Day 22 assessment. Otherwise, the tumor assessment will be classified as an unscheduled assessment and not included in the summary of overall tumor response.

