10 EFFICACY ANALYSES

10.1 Antitumor activity

The analysis of antitumor activity is exploratory in Part A1 of this study.

Tumor assessments will be performed at the Screening visit, every 8 weeks from Day 1 of Cycle 1, and at the SFU visit.

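### In both SAPs, a participant who dies before any post-Baseline scan meets two conflicting PFS rules: event at death, or censored on the date of first dose

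*SAP*

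**What the plan says.** Section 10.1.1 of the Part A SAP defines PFS as the time from first dose to objective progression "or death due to any cause, whichever occurs first". Three event and censoring sentences then follow in order.

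- Death: "Participants who die due to any cause without a documented objective disease progression will be considered to have progressed on the date of their death". Nothing requires that a scan was done.
- No scan: "Participants who do not have any post-Baseline tumor assessments will be censored on the date of their first dose of study treatment". There is no exception for death.
- Early discontinuation: "Participants who discontinue early from Part A or discontinue study treatment without documented objective disease progression or death, will be censored" at the last assessment showing no progression. Here death is excluded explicitly.

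A later rule censors participants who start other anti-cancer therapy before documented progression, at their last assessment before that therapy. The sensitivity PFS adds clinical progression as an event and uses last contact as the censoring date, but only for participants still alive without progression.

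Section 10.1.1 of the Part A1 SAP repeats these rules. Both SAPs refer to the Derivation of Efficacy Endpoints document, Version 0.6, for further detail on PFS.

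On timing, the Part A SAP places tumor assessments in "scheduled and unscheduled assessments performed between Days 21 and 28 of every even cycle of study treatment". Section 10.1 of the Part A1 SAP schedules them at Screening, then "every 8 weeks from Day 1 of Cycle 1, and at the SFU visit".

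**The concern.** The death sentence and the no-scan sentence overlap for one group: participants who die before any post-Baseline scan. One gives an event at the date of death. The other gives a censored time of 1 day. Neither SAP says which takes priority, so two programmers could code the same participant differently and each point to the text.

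The group is foreseeable. These are participants with advanced or metastatic tumors, and the first scheduled scan comes about 7 to 8 weeks after the first dose. Censoring on Day 1 is equivalent to dropping the participant from the Kaplan-Meier analysis. Those dropped have the shortest survival, so the error runs in one direction and favours the drug. Cohorts are small (3 to 6 evaluable participants per dose level in Part A, up to 8 per cohort in Part A1), so one death can visibly move a cohort's PFS rate. PFS rates at 3, 6 and 9 months are planned outputs in both SAPs.

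**Working it through.** **1. When the first scan is due.** Part A has 28-day cycles and a window of Days 21 to 28 of each even cycle, ±2 days (Section 10.1.2). Counted from Cycle 1 Day 1, the first window opens on 28 + 21 - 2 = Day 47 and closes on 28 + 28 + 2 = Day 58. This reproduces the SAP's own figure, "performed on Day 47 to 58 relative to Day 1 of Cycle 1". The target, Cycle 2 Day 22, is 28 + 22 = Day 50. In Part A1, 8 weeks from Day 1 is 56 + 1 = Day 57, and ±7 days gives Day 50 to 64, as Section 10.1.2 of that SAP states.

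**2. The two rules for one participant.** Take a death on Day 30 with no scan.

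- Death sentence: PFS = 30 days, event.
- No-scan sentence: PFS = (first dose - first dose) + 1 = 1 day, censored.

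**3. General size.** Let d be the fraction dying unscanned among those otherwise at risk after Day 1. If nobody else is censored before the last of these deaths, then at any later time S(deaths as events) = (1 - d) × S(Day 1 censoring). Day 1 censoring therefore multiplies the estimate by 1/(1 - d).

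**4. Illustrations.** All event patterns are assumed; 3 months is taken as Day 91.

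| Assumed cohort | Deaths as events | Censored on Day 1 | 1/(1-d) |
|---|---|---|---|
| 8: deaths Days 30 and 40; 3 progress Day 57; 3 progress Day 113 | 3/8 = 37.5% | 3/6 = 50.0% | 1.33 |
| 6: 1 death Day 30; 2 progress Day 50; 2 progress Day 106; 1 censored Day 162 | 3/6 = 50% | 3/5 = 60% | 1.20 |
| 6: 2 deaths Day 30; 2 progress Day 50; 1 progresses Day 106; 1 censored Day 162 | 2/6 = 33% | 2/4 = 50% | 1.50 |
| 42: 4 deaths Day 30; 15 progress Day 50; 11 progress Day 106; 12 censored Day 162 | 23/42 = 55% | 23/38 = 61% | 1.11 |

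In the first row, Day 1 censoring cuts the effective sample from 8 to 6 and the events from 8 to 6. In the second, the median moves from Day 50 to Day 106.

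**5. A range for d.** The documents give no early-death rate. Assume exponential survival with a median of m months, so that the fraction dead before Day 50 is d = 1 - 0.5^(49/(30.4375 m)).

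- m = 4: d = 24%; 10.2 deaths expected among the 42 planned for Part A; 81% chance of at least one in a cohort of 6; factor 1.32.
- m = 12: d = 9%; 3.7 deaths expected; 43% chance; factor 1.10.

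These values of d treat every death before Day 50 as unscanned. Unscheduled scans count for PFS (Part A SAP, Section 4.3), as would a scan at the Safety Follow-up visit, so the true fraction would be lower for a given survival curve.

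**The case against.** The strongest reply is that the SAP, read as a whole, points one way. PFS is defined to include death from any cause and its formula uses the date of death. The death sentence is unconditional and comes before the censoring sentences. Censoring rules ordinarily apply to people without an event. When death falls on the day other anti-cancer therapy starts, the participant stays an event, and the sensitivity PFS censors only the living. Where the authors want a death censored, as for duration of response, they say so outright. The derivation document may already settle the order.

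Most of this stands. A reader might infer from the explicit exclusion of death in the next sentence that its absence from the no-scan sentence was deliberate, and that the plan has chosen to drop early deaths. The documents do not support that: the definition, the death sentence and the sensitivity wording weigh against it, and loose drafting is at least as plausible. Nor can one conclude that the reported PFS will be biased, since that depends on how the rule is coded and on a document not at hand.

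The consequences are also limited. PFS is exploratory and untested, and is summarized only if the data allow. Dose decisions do not rest on it, and overall survival counts these deaths.

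The objection does not remove the overlap. The SAP states two incompatible results for the same participant and no precedence. Repeating the analysis in the Safety Analysis Set applies the same rules. The sensitivity PFS also changes the event definition and the censoring date, so it cannot isolate the effect. Under the literal no-scan rule, it would count as an event a death that the main PFS analysis censors on Day 1.

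**Conclusion.** The conflict is real in both SAPs, and the better-supported reading is that death before any scan is a PFS event. Applied literally, the no-scan sentence contradicts the endpoint definition and biases the Kaplan-Meier estimates upward by 1/(1-d). The size cannot be derived from the documents. The 37.5% against 50.0% comparison rests on an assumed cohort, and the range of 1.10 to 1.32 rests on assumed exponential survival with medians of 12 to 4 months and no early scans. This is an ambiguity in an exploratory, descriptive endpoint, with a known direction and a cheap cure. It is not evidence of an analysis already gone wrong.

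**What to change.** In Section 10.1.1 of both SAPs, add the condition *and have not died* to the no-scan sentence, so that first-dose censoring covers only participants with neither a post-Baseline assessment nor a death. Then add: *A death without any post-Baseline assessment is a PFS event on the date of death, unless the rule for subsequent anti-cancer therapy applies first.* Without that exception, the new text would clash with the existing rule for participants who start other therapy before dying. Someone in that position who was never scanned has no earlier assessment date, so the text should name the censoring date; first dose is the natural choice.

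Check that the Derivation of Efficacy Endpoints document gives the same order, and amend it only if it does not.

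The cost is one or two sentences per SAP and a check of the PFS program. PFS may look slightly less favourable. Living participants with no scan would still be censored at first dose, including any with early clinical progression; the sensitivity analysis already addresses those.

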Best overall response (BOR) is defined for each study participant as the best overall tumor response from each tumor assessment (scheduled and unscheduled assessments performed every 8 weeks from Day 1 of Cycle 1 (± 7 days)) according to the RECIST criteria for changes in target and non-target lesions and the appearance of new lesions. Best overall response is determined from the start of study treatment (first dose of UCB6114) until documented objective disease progression or the date of subsequent anti-cancer therapy (systemic therapy, surgery or radiotherapy for cancer), whichever occurs first. If anti-cancer therapy is started on the same day as a tumor assessment, then the overall tumor response from that assessment will be used in the derivation of BOR. If a participant does not have objective disease progression and does not start a subsequent anti-cancer therapy, then all tumor assessments (scheduled and unscheduled) up to the SFU visit will be included in the derivation of BOR. For a BOR of SD, a participant's tumor measurements must have met the SD criteria at least once after the start of study treatment at a minimum interval of no less than 49 days.

For Part A1, BOR determination requires confirmation of CR or PR responses at a subsequent assessment ≥ 4 weeks (28 days) after the criteria for CR or PR responses are first met, however, an unconfirmed BOR will also be derived for each participant for the purpose of reporting (as

described below in [Section 10.1.2](#)). Table C in Appendix 11.9 of the protocol and Table 1 and subsequent text in the Derivation of Efficacy Endpoints document provides detail on the derivation of BOR when confirmation of CR and PR responses is required. The definition of an unconfirmed BOR is also included in this document. Although the derivation of unconfirmed BOR does not include the requirement for a CR or PR response to be confirmed ≥ 4 weeks (28 days) after the initial response, a participant's CR or PR response may, in fact, be confirmed at a subsequent assessment ≥ 4 weeks (28 days) after the criteria for the CR or PR response are first met.

Confirmed BOR and unconfirmed BOR will be derived programmatically based on the overall tumor assessment data recorded on the eCRF by the investigator.

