Progression-free survival (PFS) will be calculated as the time in days from the first dose of study treatment to the date of the first documented objective disease progression (i.e. according to the RECIST guidelines), or death due to any cause, whichever occurs first. The following calculation will be performed:

$$PFS = (\text{Date of Objective Progressive Disease/Death} - \text{Date of First Dose}) + 1$$

Participants who die due to any cause without a documented objective disease progression will be considered to have progressed on the date of their death. Participants who do not have any post-Baseline tumor assessments will be censored on the date of their first dose of study treatment. Participants who discontinue early from Part A1 or discontinue study treatment without documented objective disease progression or death, will be censored on the date of their

last available (scheduled or unscheduled) tumor assessment at which a lack of objective disease progression was determined. Participants who start anti-cancer therapy during Part A1 without a prior documented objective disease progression will be censored on the date of their last available (scheduled or unscheduled) tumor assessment prior to the initiation of the subsequent anti-cancer therapy. If anti-cancer therapy starts on the same date as the participant's tumor assessment and determination of objective disease progression, or the participant's death (due to any cause), then the participant will not be censored and the participant will be included as having an uncensored event on this date. This censoring rule will also be applied to participants who are ongoing at any data cut-off for an analysis of Part A1 data who have no documented objective disease progression. The use of anti-cancer therapy during Part A1 will be identified via ongoing medical review of the concomitant medications together with the start dates of further anti-cancer therapy information recorded on the survival follow-up pages of the eCRF.

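### Exploratory PFS: on a date reading, a scan on the day new anti-cancer therapy starts counts if it shows progression and is dropped if it does not, while BOR uses it either way

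*SAP*

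**What the plan says.** Both SAPs set the rules in Section 10.1.1.

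- **PFS, new therapy.** Without earlier objective progression, the Part A SAP censors at "their last available (scheduled or unscheduled) tumor assessment prior to the initiation of the subsequent anti-cancer therapy". The Part A1 SAP uses the same rule: "last available (scheduled or unscheduled) tumor assessment prior to the initiation of the subsequent anti-cancer therapy".
- **PFS, same-date exception.** The first trigger is "If anti-cancer therapy starts on the same date as the participant's tumor assessment and determination of objective disease progression"; the second is death on that date. In either case "the participant will not be censored and the participant will be included as having an uncensored event on this date". A same-day scan without progression is not mentioned.
- **PFS, stopping treatment.** A participant who leaves the study part or stops study treatment without progression or death is censored at the last scan that showed no progression.
- **PFS, fallback.** Censoring at first dose applies to participants with no post-Baseline tumor assessment.
- **PFS, sensitivity analysis.** It adds clinical progression as an event and inherits the new-therapy rule.
- **BOR.** Part A: "If anti-cancer therapy is started on the same day as a tumor assessment, then the overall response from that assessment will be used". Part A1: "If anti-cancer therapy is started on the same day as a tumor assessment, then the overall tumor response from that assessment will be used". Neither sets a condition on the result.

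For further detail on PFS, both SAPs refer to the Derivation of Efficacy Endpoints document, Version 0.6.

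**The concern.** Whether a scan is admitted to a time-to-event analysis should not depend on what it shows. Here a same-day scan with progression adds an event, while a same-day scan without progression is set aside and the participant leaves the risk set at an earlier scan. Where this matters at all, it can only lower the Kaplan-Meier PFS estimate.

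The same scan is also handled differently for two endpoints in one section. A participant may count as having disease control on a scan that PFS ignores, or have an unconfirmed response dated after PFS was censored. The authors foresaw the coincidence, since they wrote same-day rules for both endpoints, but the PFS rule covers only the event side.

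**Working it through.** The plan states no figure on this point, so there is none to reproduce. The check applies the rules as written to the Part A scan schedule and then works a small illustration.

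**Scan days.** Part A SAP Section 10.1.2 assigns assessments to Day 22 of each even 28-day cycle.
- Cycle 2: (2 − 1) × 28 + 22 = Day 50.
- Cycle 4: (4 − 1) × 28 + 22 = Day 106.
- Interval: 106 − 50 = 56 days.

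**One participant: SD on Day 50, scan and new therapy both on Day 106.**

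| Day 106 scan | PFS, new-therapy rule by date | PFS, stopping-treatment rule | PFS, on-or-before rule | Scan used for BOR? |
|---|---|---|---|---|
| Progression | Event, Day 106 | Not applicable | Event, Day 106 | Yes |
| SD | Censored, Day 50 | Censored, Day 106 | Censored, Day 106 | Yes |
| First PR | Censored, Day 50 | Censored, Day 106 | Censored, Day 106 | Yes |

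The stopping-treatment column assumes study treatment has stopped and there is no later scan. The two censoring rules give dates 56 days apart, assuming no unscheduled scan in between.

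**Unconfirmed response.** In the last row, duration of unconfirmed response starts on Day 106, which is 56 days after PFS was censored. The response cannot become a confirmed BOR: confirmation needs a further scan at least 28 days later, and BOR assessment ends when new therapy starts.

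**Only post-Baseline scan is the same-day one (Day 50).** No scan precedes therapy, and the first-dose fallback does not apply because a post-Baseline scan exists. The new-therapy rule gives no date; the on-or-before rule gives Day 50. The same scan can put the participant in DCR if it meets the SD minimum interval.

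**Kaplan-Meier illustration at Day 106.** Assume N participants, all progression-free on Day 50. On Day 106, k progress and m have a same-day scan without progression; the rest continue.
- As written: (N − m − k)/(N − m)
- On or before: (N − k)/N

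| N | k | m | As written | On or before |
|---|---|---|---|---|
| 6 | 1 | 1 | 4/5 = 0.800 | 5/6 = 0.833 |
| 6 | 2 | 1 | 3/5 = 0.600 | 4/6 = 0.667 |
| 6 | 2 | 2 | 2/4 = 0.500 | 4/6 = 0.667 |
| 6 | 1 | 3 | 2/3 = 0.667 | 5/6 = 0.833 |
| 6 | 2 | 4 | 0/2 = 0.000 | 4/6 = 0.667 |
| 3 | 1 | 1 | 1/2 = 0.500 | 2/3 = 0.667 |
| 8 | 1 | 1 | 6/7 = 0.857 | 7/8 = 0.875 |

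Section 2.3 of each SAP gives the cohort sizes: 3 to 6 evaluable participants in Part A and up to 8 in Part A1. The values of k and m are assumptions. With no event after the earlier scan and up to the same-day scan, the two rules give the same estimate.

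**The case against.** The strongest reply is that the text does not plainly drop the scan. A participant who stops study treatment and moves to another therapy also fits the stopping-treatment sentence, which would censor at the same-day scan. This stands: there are two overlapping rules without precedence, and a reader who infers that the program will certainly discard the scan goes beyond the text.

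Second, a scan done in the morning before therapy starts that afternoon is prior to it by clock time. That reading is possible, but the PFS rules work in dates. If same-day scans already counted as prior, the progression half of the exception would hardly be needed.

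Third, the Derivation of Efficacy Endpoints document may settle the tie. It is not available here, so what will be programmed is unknown. The SAP states the rule itself, however, and its text should agree with its own BOR rule.

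Fourth, a reader might infer that responses in general can begin after PFS censoring. Only unconfirmed ones can. Nor is this the only way the endpoints diverge: Section 10.1.1 gives DOR no new-therapy censoring rule, so DOR may run past PFS censoring in any case. The change proposed here leaves that alone.

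Finally, antitumor activity is exploratory, PFS is summarized descriptively if the data allow, and no PFS comparison is planned. This stands and limits the weight of the point.

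**Conclusion.** The point holds as a minor defect of wording. On a date reading, the new-therapy rule makes use of a same-day scan depend on its result and conflicts with the BOR rule. It also overlaps, without precedence, with the stopping-treatment rule, and gives no censoring date when the same-day scan is the only one.

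The size is not known. The documents give no frequency for such coincidences, and they should be few. The Kaplan-Meier figures show that one case can move an estimate in cohorts of 3 to 8; they do not estimate a bias in this trial. A reader might also work the example at the first scheduled scan and quote a figure for the rule as written. The documents do not support that, because the new-therapy rule defines no censoring date there. Nothing here touches confirmed response or the primary safety endpoints.

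**What to change.** In Section 10.1.1 of both SAPs:

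1. Censor PFS at the last tumor assessment *on or before the date of initiation of* the subsequent anti-cancer therapy, in place of the wording that requires the scan to come before initiation.
2. Keep the rule that progression or death on the same date is an event.
3. State that the new-therapy rule takes precedence over the stopping-treatment rule.
4. Apply the same text to the sensitivity PFS, and check that the Derivation of Efficacy Endpoints document agrees.

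A same-day scan is then used whatever it shows, as in BOR, and a participant whose only scan is the same-day one has a censoring date. The cost is a few words in each SAP and one inequality in the program, with no new data collection.
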